7.2.1 Pre-Existing Conditions

All pre-existing conditions that meet the criteria specified below will be entered into Medical History eCRFs.

- All medical conditions of any grade occurring or ongoing within 48 hours prior to the first infusion of RDV.
- Arm 1: Major obstetrical diagnoses during the current pregnancy prior to start of RDV infusions.
- Arm 1: Gestational age at 48 hours prior to first infusion.
- Hospitalization for COVID-19

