2.1 Study Design

IMPAACT 2032 is a Phase IV prospective, open label, non-randomized opportunistic study to describe the pharmacokinetic (PK) properties and safety of remdesivir (RDV) administered intravenously as part of clinical care among hospitalized pregnant and non-pregnant women with coronavirus disease of 2019 (COVID-19). RDV will be provided and managed by the participant's treating physician and will not be provided as part of this study. This study is comprised of 2 arms specific to the study population. Arm 1 includes pregnant women, while Arm 2 includes non-pregnant women of childbearing potential. PK sampling will be performed during the RDV infusions and women will be followed for safety for 4 weeks after the last infusion; Arm 1 women who are still pregnant at that time will have an additional follow-up at the time of delivery.

The target sample size is 20 PK-evaluable women for each arm (defined in **Section 4** below). If a participant is deemed unevaluable for PK, the Clinical Management Committee (CMC) will determine how to proceed with replacement. There is no randomization or stratification in this study.

The primary and secondary objectives are to describe the pharmacokinetics of RDV and its metabolite, GS-441524, in plasma after administration to pregnant and non-pregnant women as part of clinical care and to describe clinical and laboratory safety outcomes through 4 weeks postlast infusion in pregnant and non-pregnant women receiving RDV as part of clinical care and during delivery in pregnant women. Other objectives that will be addressed in separate SAP(s) are listed in Section 2.2 of the protocol (Version 2.0).

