2.5 Formal Interim Monitoring

No formal interim analyses were planned or specified in the study protocol. The plans for study monitoring are described in Section 9.5 of the protocol (Version 2.0).

3 Outcome Measures

3.1 **Primary Outcome Measures (Arm 1)**

- 1. [For Primary Objective 1] Non-compartmental PK parameters:
 - a. RDV area under the plasma concentration-time curve (AUC)
 - b. RDV half-life (t_{1/2})
 - c. GS-441524 trough concentration (Ctrough)
- 2. [For Primary Objective 2] Clinical and laboratory safety outcomes:
 - a. Maternal renal adverse events of any grade through 7 days post-last infusion
 - b. Maternal hepatic adverse events of any grade through 7 days post-last infusion
 - c. Maternal hematologic events of any grade through 7 days post-last infusion
 - d. Adverse events through 4 weeks post-last infusion and during delivery:
 - i. Maternal Grade 3 or higher adverse events
 - ii. Serious adverse events
 - iii. Maternal Grade 3 or higher adverse events assessed as related to RDV by the CMC
 - e. Labor/delivery outcomes:
 - i. Pregnancy loss
 - ii. Congenital anomalies
 - iii. Preterm birth (< 37 weeks, < 34 weeks)
 - iv. Small for gestational age (SGA) (< 10th percentile for gestational age)
 - f. Newborn physical exam:
 - i. Birth weight
 - ii. Length
 - iii. Head circumference

Note: Additional non-compartmental PK parameters, described in Table 2 of the PK SAP, will also be summarized for Arm 1 as part of the Primary Analysis Report for RDV, GS-441524, and/or GS-704277 (data permitting).

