through 4 weeks post-last infusion and during	
delivery:	
1. Maternal Grade 3 or higher adverse events	
2. Serious adverse events	
3. Maternal Grade 3 or higher adverse	
events assessed as related to RDV by	
the CMC	
(C) Occurrence of each of the following	
labor/delivery outcomes*:	
1. Pregnancy loss	
 Congenital anomalies Preterm birth < 37 weeks 	
4. Preterm birth < 34 weeks	
5. Small for gestational age (SGA) (< 10 th	
percentile for gestational age)	
······································	
*For multiple births, the "worst" outcome within	
the sibling set will be used.	
Handling of intercurrent events	Handling of missing data
The following intercurrent events are relevant	Missing data will be handled using an
to the estimand:	"available case" approach. Outcome
 Maternal death Terminal fetus/infant event 	measures for participants who discontinue
	follow-up before the time point of interest (i.e., 7 days post-last infusion/4 weeks post-
Maternal death will be addressed using a	last infusion and delivery) and did not have
composite event approach.	an event of interest will be missing (i.e.,
	these participants will not be included in the
Terminal fetus/infant event will be addressed	denominator).
as a composite event for pregnancy loss. A	
principal stratum approach will be used for	Labor/delivery outcome measures for
congenital anomalies, preterm birth, and SGA.	participants who discontinued follow-up
	before delivery will not be included (i.e.,
	missing observations that would be relevant

A supplementary analysis that applies a principal stratum approach for maternal death will be used for relevant outcome measures.	to the variable are considered missing completely at random). As a sensitivity analysis, we will use multiple imputation over a range of potential probabilities, including "best case" (i.e., probability of event = 0) and "worst case" (i.e., probability of event = 1) scenarios.
Population-level summary measure	Analysis approach
(A) Probability of a pregnant woman, who received any amount of RDV for the treatment of COVID-19, having at least one adverse event (maternal renal/hepatic/hematologic of any grade) through 7 days post last infusion	(A) Proportion of participants with at least one adverse event (maternal renal/hepatic/hematologic of any grade) through 7 days post last infusion, bounded by an exact 95% CI

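### SAP 5.1.2: the worst-case imputation for preterm birth can score women as preterm who are already known to be undelivered past 34 or 37 weeks

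*SAP*

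**What the plan says.** SAP 3.1 lists among the primary Arm 1 outcomes "Preterm birth (< 37 weeks, < 34 weeks" as two cut-offs, and SAP 5.1.2 (set C) treats them as separate variables.

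For missing data, SAP 5.1.2 gives a general available-case rule: a woman who leaves before the time point of interest without an event is missing, that is, "these participants will not be included in the" denominator. It then gives one rule for all labor/delivery outcomes: measures from women who stopped follow-up "before delivery will not be included (i.e", with missingness called completely at random. The sensitivity analysis follows: "As a sensitivity analysis, we will use multiple imputation over a range of potential probabilities". The range includes a best case (probability 0) and a worst case ("probability of event = 1) scenarios"). No part of this cell refers to gestational age at last contact.

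Two other places show what is known about these women. Protocol 7.2.1 records "Arm 1: Gestational age at 48 hours prior to first infusion". SAP 2.1 says that "Arm 1 women who are still pregnant at that time will have an additional follow-up at the time of delivery", where the time meant is the end of the 4-week follow-up. Sites must therefore know at 4 weeks who is still pregnant.

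**The concern.** Congenital anomalies and SGA need a birth before they can be assessed, so an undelivered woman who leaves is truly missing for them. Preterm birth is different. Once a pregnancy is documented as ongoing at 34+0 weeks, a birth before 34 weeks can no longer happen, and the same holds at 37+0 for the other cut-off. For that variable she is an observed 'no'.

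A sensitivity range should span what is unknown. Here the upper end includes preterm births that cannot have occurred, so the range overstates the uncertainty caused by loss to follow-up. The affected outcomes are primary, and SAP 1.1 intends them for the primary manuscript and ClinicalTrials.gov.

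A lesser point is that the SAP does not say whether the two cut-offs are imputed together. With separate draws at intermediate probabilities, a woman could be imputed as a birth before 34 weeks but not before 37.

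**Working it through.** **1. The plan's own figure.** The SAP uses exact (Clopper-Pearson) 95% intervals. For 4/20, SAP Table 2 gives 6% to 44%; recomputation gives 5.7% to 43.7%. All 18 rows of that table reproduce. The documents state no figure for the missing-data rule, so its effect has to be illustrated.

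**2. Can the situation arise?** Arm 1 enrolls at any gestational age (Protocol 4.1.2). Days from first infusion to the 4-week timepoint = (number of daily infusions − 1) + 28.

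- 5 infusions: 4 + 28 = 32 days. For 37+0: 259 − 32 = 227 days = 32w3d. For 34+0: 238 − 32 = 206 days = 29w3d.
- 10 infusions: 9 + 28 = 37 days. For 37+0: 259 − 37 = 222 days = 31w5d. For 34+0: 238 − 37 = 201 days = 28w5d.

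A woman first infused at or after these gestational ages, and still pregnant at 4 weeks, is a known 'no' for that cut-off. A woman who enters at 37 weeks or later cannot have the outcome at all. Protocol 6.5 collects no routine data between the 4-week timepoint and delivery, so women can be lost in that gap.

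**3. Effect on the worst case.** Let N be the women in the arm, x the observed preterm births and k the women lost before delivery but last seen at or past the threshold. Suppose no one else is missing.

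- Worst case as written: (x + k)/N
- With known status used: x/N
- Excess: k/N, or 4 points per woman at N = 25 and 5 points at N = 20

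N = 25 is the initial enrollment limit (Protocol 9.4.2). With x = 4 (assumed), the worst case is 20.0%, 24.0%, 28.0% and 36.0% for k = 1, 2, 3 and 5, against 4/25 = 16.0% in each case.

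**4. Mixed illustration (counts assumed).** 25 women are treated and 22 have delivery data, with 4 births <37 weeks, of which 2 are <34. Three are lost after the 4-week timepoint, all last seen past 34 weeks and two past 37. There are no maternal deaths or terminal fetal events.

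| Outcome | Best case | Worst case as written | Worst case, unknowns only |
|---|---|---|---|
| <37 weeks | 4/25 = 16.0% | (4+3)/25 = 28.0% (12.1–49.4) | (4+1)/25 = 20.0% (6.8–40.7) |
| <34 weeks | 2/25 = 8.0% | (2+3)/25 = 20.0% (6.8–40.7) | 2/25 = 8.0% (1.0–26.0) |

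For <37 weeks the best-to-worst range shrinks from 12 points to 4. For <34 weeks it shrinks from 12 points to none, because nothing is unknown.

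**The case against.** **The worst case is meant to be extreme.** It is paired with a best case, and the objectives are descriptive. That is fair as to importance. But an extreme bound should still be a possible one, and the best case does not repair it: probability 0 is right for these women but is also applied to women whose outcome is truly unknown.

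**She is not a known non-event for the whole estimand.** This stands. The description of estimand C also counts pregnancy loss or death. The intercurrent-event cell makes maternal death a composite event and uses a principal stratum for terminal fetus/infant events. A woman last seen at 37 weeks could later die or have a stillbirth. Only the preterm-birth component is known.

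**Pregnancy status is not a listed item.** Protocol Table 5 does not name it at the safety follow-up timepoints, and no final evaluation is required on withdrawal (Protocol 4.7). Status at 4 weeks is nevertheless needed to decide who is followed to delivery. For women who leave earlier, it depends on what the record shows.

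**Nesting is unspecified, not shown to be wrong.** At probabilities 0 and 1, applied to both cut-offs, no conflict can occur. Coding detail is left to the Analysis Implementation Plan, which was not available.

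**A stronger reading.** A reader might infer that the primary proportion is biased upward, because only women still pregnant can be dropped, and that known non-events should be put back in the denominator. The documents do not establish this; it depends on why delivery data are missing. Two assumed cases, with true risk 20%:

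- 20% of delivery records lost completely at random, as the SAP assumes. Available-case: (0.20 × 0.80)/0.80 = 20.0%, unbiased. If 30% of women are past the threshold at last contact, adding back those who were lost gives 0.16/(0.80 + 0.20 × 0.30) = 0.16/0.86 = 18.6%, too low.
- All preterm births captured and 20% of term deliveries lost. Available-case: 0.20/(0.20 + 0.80 × 0.80) = 0.20/0.84 = 23.8%, too high. Adding back moves it toward 20%.

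The denominator change is a trade-off, not a correction.

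**Conclusion.** The concern holds for the sensitivity analysis of the two preterm outcomes. As written, the worst case assigns a preterm birth to women whose gestational age at last contact rules it out. This inflates the upper bound by k/N: 4 points per such woman in an arm of 25. In the mixed illustration the excess is 8 points for <37 weeks (28% against 20%) and 12 points for <34 weeks (20% against 8%).

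This rests on reading the imputation range as applying to all women with missing outcomes, since the SAP states no restriction, and on assumed counts. The documents give no rate of loss before delivery, so the number affected may be small or zero. The conclusion covers the preterm-birth component only, not later maternal death or pregnancy loss. It does not extend to the primary available-case estimate, for which upward bias is not shown. Nor does it extend to anomalies or SGA, where exclusion is reasonable. Women who die before delivery are unaffected, because death already counts as an event.

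**What to change.** Add to the missing-data cell of SAP 5.1.2, for preterm birth in set C:

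- In the multiple-imputation sensitivity analysis, set the preterm-birth component to no event for <34 (<37) weeks for any woman whose baseline gestational age plus elapsed time shows her undelivered at or after 34+0 (37+0) weeks at last contact.
- Impute only women last known pregnant before the threshold.
- Impute the two cut-offs jointly, so that a birth <34 weeks is always also a birth <37 weeks.
- Leave later maternal death and pregnancy loss to the intercurrent-event rules.

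Keep the primary available-case denominator and the rules for the other labor/delivery outcomes. A version that counts known non-events may be reported as an additional sensitivity analysis, labelled with the direction in which it can err.

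The cost is a few lines of SAP text and one derived variable: gestational age when last documented as undelivered. It uses gestational age and contact dates already collected. The elapsed time must run from the point at which gestational age is recorded, 48 hours before the first infusion. A woman without documentation that she was still pregnant at the threshold stays missing and is imputed.

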Participants will be pregnant and non-pregnant women hospitalized for COVID-19 and will receive daily RDV infusions, typically for 5 days but in some cases for up to 10 days, as part of their clinical care. RDV will be provided and managed by the participants' treating physician and will not be provided as a part of this study. Women may be enrolled prior to starting RDV or after starting RDV but must be enrolled prior to the start of the 4th infusion. Participants will undergo intensive PK sampling on the day of the 3rd, 4th, or 5th infusion (at site discretion), as described in Section 6.4.1. Protein binding capacity of RDV will also be assessed ex vivo from the pre-dose intensive PK sample. Participants will also undergo collection of single PK samples with standard of care (SOC) labs drawn on the days of the 2nd, 3rd, 4th, and 5th infusions (with the exception of the day of intensive PK sampling), and also at 48 hours after the last infusion, as described in Section 6.4.2. For Arm 1 participants, maternal and cord blood PK sampling will be performed at delivery for a comparison of maternal and fetal plasma RDV concentrations if the participant received RDV infusion within the preceding 5 days. Additionally, for women in both Arms who are lactating, and who consent to this sample collection, an optional breast milk sample may be collected on the intensive PK sampling day and at 48-hours after the last RDV infusion, to assess breast milk concentrations of RDV and its metabolites.

For all women, clinical and laboratory evaluations will be abstracted from the medical record. Pregnancy, birth, and infant outcomes will be obtained from pregnant women enrolled in Arm 1. See Appendix I and Section 6 for additional details. Arm 1 and Arm 2 participants will be followed through 4 weeks after the last infusion of RDV; Arm 1 women who are still pregnant at that time will have additional follow-up at the time of delivery.

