4.1 Inclusion Criteria – Arm 1 (Pregnant Women)

Women must meet all of the following inclusion criteria to be enrolled in Arm 1.

4.1.1 Of legal age or otherwise able to provide independent informed consent as determined by site SOPs and consistent with all applicable IRB policies and procedures, and is willing and able to provide informed consent for her own participation in this study.

Or

Of legal age to provide independent informed consent but is unable to provide informed consent (e.g. impaired capacity, as determined by site SOPs and consistent with all applicable IRB policies and procedures) and a Legally Authorized Representative (LAR) is willing and able to provide written informed consent on behalf of the participant in accordance with 21 CFR 50.27.

Note: All sites must follow the policies and procedures of all applicable IRBs; this includes single IRB (sIRB) policies and procedures. Refer to Section 13.1 for more information on sIRB oversight.

- **4.1.2** At study entry, viable intra-uterine pregnancy of any gestational age, based on medical records.
- **4.1.3** At study entry, hospitalized AND has confirmed or suspected COVID-19, based on medical records.
- **4.1.4** At study entry, receiving or expected to receive RDV for COVID-19 clinical care, as prescribed by the clinical care provider and documented in medical records.

Note: The study investigator or designee will confirm that a potential study participant is receiving or expected to receive RDV based on information in the medical record.

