4.2 Inclusion Criteria – Arm 2 (Non-Pregnant Women)

Women must meet all of the following inclusion criteria to be enrolled in Arm 2.

4.2.1 Of legal age or otherwise able to provide independent informed consent as determined by site SOPs and consistent with all applicable IRB policies and procedures, and is willing and able to provide informed consent for her own participation in this study.

Or

Of legal age to provide independent informed consent but is unable to provide informed consent (e.g. impaired capacity, as determined by site SOPs and consistent with all applicable IRB policies and procedures) and a LAR is willing and able to provide written informed consent on behalf of the participant in accordance with 21 CFR 50.27.

Note: All sites must follow the policies and procedures of all applicable IRBs; this includes sIRB policies and procedures. Refer to Section 13.1 for more information on sIRB oversight.

- **4.2.2** At study entry, between 18 and 45 years of age, based on medical records and participant report.
- **4.2.3** Assigned female at birth and at study entry not taking cross-sex hormone therapy.
- **4.2.4** At study entry, not suspected to be pregnant, based on participant report and/or investigator or designee determination.
- **4.2.5** At study entry, hospitalized AND has confirmed or suspected COVID-19, based on medical records.
- **4.2.6** At study entry, receiving or expected to receive RDV for COVID-19 clinical care, as prescribed by the clinical care provider and documented in medical records.

Note: The study investigator or designee will confirm that a potential study participant is receiving or expected to receive RDV based on information in the medical record.

4.3 Exclusion Criteria – Arms 1 and 2

Women who meet any of the following criteria will be excluded from enrolling in this study:

- **4.3.1** At study entry, has started or received the 4th RDV infusion.
- **4.3.2** At study entry, evidence of post-menopausal status (medical or surgical), based on medical records and/or participant report.
- **4.3.3** At study entry, any contraindications to RDV treatment for COVID-19, based on investigator or designee determination.
- **4.3.4** Received or administered any disallowed medications listed in Section 5.4 within 48 hours prior to study entry.

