5.1.2 Second Primary Estimand

Primary Objective 2: To describe the clinical and laboratory safety outcomes through 4 weeks post-infusion and during delivery in pregnant women receiving RDV as part of				
clinical care. Estimand description	(A) Probability of a pregnant woman, who received any amount of RDV while hospitalized for the treatment of COVID-19,* having at least one adverse event (maternal renal/hepatic/hematologic of any grade) or death through 7 days post-last infusion.			
	(B) Probability of a pregnant woman, who received any amount of RDV while hospitalized for the treatment of COVID-19,* having at least one adverse event (maternal Grade 3 or higher/serious/maternal Grade 3 or higher assessed as related by the CMC) or death through 4 weeks post-last infusion and at delivery.			
	(C) Probability of a pregnant woman, who received any amount of RDV while hospitalized for the treatment of COVID-19,* having a labor/delivery outcome (pregnancy loss/congenital anomalies/preterm birth < 37 weeks/preterm birth < 34 weeks/SGA), pregnancy loss, or death.			
	*NOTE: This study design is opportunistic in that it enrolls women who may have already received at least one infusion of RDV. Because participants can be enrolled any time prior to the 4 th infusion, the study population will potentially not include women who started RDV and discontinued it prior to the 4 th infusion due to toxicity, intolerance, virologic failure, or any other reason. Consequently, the results may be overly optimistic.			
Treatment	Remdesivir (RDV)			
Target population		Analysis set		
	n who received any amount of talized for treatment of	Pregnant women who received any amount of RDV (Safety analysis set)		
that it enrolls wo	dy design is opportunistic in men who may have already one infusion of RDV.			

Because participants can be enrolled any time	
prior to the 4 th infusion, the study population	
will potentially not include women who started	
RDV and discontinued it prior to the 4 th	
infusion due to toxicity, intolerance, virologic	
failure, or any other reason. Consequently, the	
results may be overly optimistic.	
Variable(s)	Outcome measure(s)
(A) Occurrence of each of the following	Outcome measures as defined by the
through 7 days post-last infusion: 1. Maternal renal adverse events of any	variables
grade	
2. Maternal hepatic adverse events of	
any grade	
3. Maternal hematologic adverse events	
of any grade	
(B) Occurrence of each of the following	

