(B) Probability of a pregnant woman, who received any amount of RDV for the treatment of COVID-19, having at least one adverse event (maternal Grade 3 or higher/serious/maternal Grade 3 or higher assessed as related by the CMC) through 4 weeks post last infusion and at delivery	 (B) Proportion of participants with at least one adverse event (maternal Grade 3 or higher/serious/maternal Grade 3 or higher assessed as related by the CMC) through 4 weeks post last infusion, bounded by an exact 95% Cl
(C) Probability of a pregnant woman, who received any amount of RDV for the treatment of COVID-19, having at least one labor/delivery outcome (pregnancy loss/congenital anomalies/preterm birth < 37 weeks/preterm birth < 34 weeks/SGA)	(C) Proportion of participants with at least one labor/delivery outcome (pregnancy loss/congenital anomalies/preterm birth < 37 weeks/preterm birth < 34 weeks/SGA), bounded by an exact 95% Cl

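### SAP 5.1.2 (C) keeps women already past 34 or 37 weeks in the preterm-birth denominators and gives no number at risk; add the at-risk count and proportion beside the planned ones.

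*SAP*

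**What the plan says.** Preterm birth below 37 and below 34 weeks are primary safety outcomes for Arm 1 (Protocol 9.2, Table 7; SAP 3.1). SAP 5.1.2 (C) estimates them as follows: "Proportion of participants with at least one labor/delivery outcome (pregnancy loss/congenital anomalies/preterm birth < 37 weeks/preterm birth < 34 weeks/SGA), bounded by an exact" 95% CI. The Variable(s) row lists each outcome separately, so I read this as one proportion per outcome.

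The analysis set is "Pregnant women who received any amount of RDV (Safety analysis set"). Protocol 4.1.2 admits a "viable intra-uterine pregnancy of any gestational age". Two rules in 5.1.2 alter the denominator:

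- Missing data: delivery outcomes of women who leave follow-up "before delivery will not be included".
- Terminal fetus/infant event: a principal stratum approach is used for "congenital anomalies, preterm birth, and SGA". I take this to remove such pregnancies from the preterm proportions.

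Maternal death is counted as an event (composite approach). The estimand description for (C), however, ends "birth < 34 weeks/SGA), pregnancy loss, or death", which on its face makes pregnancy loss an event for every outcome in the list, preterm birth included.

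On timing, Protocol section 3 states: "Women may be enrolled prior to starting RDV or after starting RDV but must be enrolled prior to the start of the 4th infusion". Exclusion 4.3.1 matches this. Under Protocol 4.7 a woman may be discontinued if RDV has not started within 7 days of entry, so entry can also come before the first infusion.

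SAP section 4 and Protocol 9.6 add a display by trimester. SAP 1.1 leaves table layouts and coding to an Analysis Implementation Plan, which was not available for this review.

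**The concern.** A woman first treated at 38 weeks cannot have a birth before 37 weeks, and one treated at 35 weeks cannot have a birth before 34. Nothing in 5.1.2 counts these women separately. They enter as non-events, unless they count through maternal death or, on the wording of the estimand description, through pregnancy loss.

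The reported figure therefore mixes two things: how late in pregnancy women were treated, and how often the remaining women delivered preterm. The effect runs in one direction, towards a lower proportion and a lower upper limit. It matters most when few or no preterm births are seen, because the upper limit is then the main information the study offers on the outcome.

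The SAP already warns that results may look too favourable because women can enter after several infusions. Late treatment relative to gestation pushes the same way for preterm birth, and the SAP does not mention it.

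**Working it through.** **1. The plan's own figure.** Exact (Clopper-Pearson) 95% limits for x events in n women are the 2.5% quantile of Beta(x, n − x + 1) and the 97.5% quantile of Beta(x + 1, n − x). For 4/20 this gives 5.7% to 43.7%, matching the stated 6% to 44%. All 18 rows of SAP Table 2 (Protocol Table 10) reproduce. That table concerns Grade 3 or higher events or adverse pregnancy outcomes; neither document gives a precision figure for preterm birth itself.

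**2. Effect of women past the cut-off.** Let N be the women with delivery data, k those already past the cut-off, and f = k/N. If none of the k women counts through death or pregnancy loss, then

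planned proportion = x/N = [x/(N − k)] × (1 − f).

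The documents do not give f. It may be zero, and it may differ between cut-offs: the share past 34 weeks is at least the share past 37. The table assumes N = 20.

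| f | n at risk | 2 events: % (95% CI) | 0 events: upper 95% limit |
|---|---|---|---|
| 0 (same as planned) | 20 | 10.0 (1.2–31.7) | 16.8% |
| 10% | 18 | 11.1 (1.4–34.7) | 18.5% |
| 20% | 16 | 12.5 (1.6–38.3) | 20.6% |
| 50% | 10 | 20.0 (2.5–55.6) | 30.8% |

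The planned result is the first row whatever f is.

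**3. The trimester display.** Neither document defines trimester boundaries. If the third trimester starts before 34 weeks, all women past a cut-off fall in that row, so the earlier rows are unaffected. Within the row the mixture remains. Assume 10 of the 20 women and both events fall there:

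- none past the cut-off: 2/10 = 20.0% (2.5–55.6)
- 2 past it (overall f = 10%): 2/8 = 25.0% (3.2–65.1)
- 4 past it (overall f = 20%): 2/6 = 33.3% (4.3–77.7)

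**4. Can the at-risk set be derived from collected data?** Gestational age is recorded at 48 hours before first infusion (Protocol Table 2 and 7.2.1), infusion dates in Table 3, enrolment in the Subject Enrollment System (4.5), and infant gestational age and birth date in Table 6.

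The natural starting point is the later of first infusion and entry. Entry requires an ongoing pregnancy, so a woman who enters after her first infusion cannot have delivered before entry. A woman who enters first is unexposed until she is infused.

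Gestational age then = recorded value + 2 days + days from first infusion to any later entry. With once-daily infusions and entry no later than just before the 4th, the last term is 0 to 3 days, so 2 to 5 days are added. The recorded value must therefore be below:

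- 36w5d (2 days added) to 36w2d (5 days added) for the 37-week cut-off;
- 33w5d to 33w2d for the 34-week cut-off.

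If only completed weeks are recorded:

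- 35 weeks becomes 35w2d to 36w4d, always below 37w0d;
- 36 weeks becomes 36w2d to 37w4d, ambiguous;
- 37 weeks becomes at least 37w2d, always past.

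The same holds for 32, 33 and 34 weeks against 34w0d. Only one recorded value per cut-off is ambiguous.

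**The case against.** The strongest reply is that nothing is wrong. The target population is stated as pregnant women who received any RDV, the study is descriptive with no hypotheses (SAP 2.2), and the proportion with its exact interval is correct for that population. That stands. A reader might infer that the planned figure is biased or its interval too narrow. The documents do not support this: it holds only if the planned estimand is replaced by risk among women below the cut-off, which the SAP does not claim to estimate.

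Second, gestational age is not ignored. The SAP adds the trimester display because any gestational age can enrol, the report has a baseline section, and the Analysis Implementation Plan may already show numbers at risk. This stands in part. The display states no split at 34 or 37 weeks, and a denominator that defines what is estimated belongs in the SAP, which sets the estimands. Absence from the SAP does not prove absence from the Analysis Implementation Plan.

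Third, a reader might infer that women past a cut-off can count only through maternal death. That follows from the intercurrent-event row but not from the estimand description, which adds pregnancy loss. The text does not settle which applies.

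Fourth, the size rests wholly on an assumed f. At 10% to 20% the shift is small beside the width of the interval, and the large changes need assumptions such as half the women past the cut-off. This stands.

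Fifth, an at-risk proportion still treats a woman at 36w6d like one at 12 weeks. This also stands, and is why the gestational-age distribution should appear beside it.

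**Conclusion.** The point holds as a reporting gap in two primary safety outcomes, not as an error in the planned interval. The SAP text contains neither a number at risk nor a proportion among women who could still have the event, although eligibility allows women past either cut-off.

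The direction is certain if any such woman enrols and does not count through death or pregnancy loss: the planned proportion is then (1 − f) times the at-risk proportion. The size is unknown. With 20 women and no events, the upper limit is 16.8% as planned, against 20.6% if 4 women are past the cut-off and 30.8% if 10 are. If none is past it, nothing changes.

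Separately, the estimand description and the intercurrent-event row of 5.1.2 disagree on whether pregnancy loss is an event for preterm birth. They need to be reconciled whatever is decided on the denominator.

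**What to change.** Keep the planned proportions. First reconcile the estimand description and the intercurrent-event row on pregnancy loss. Then add to SAP 5.1.2 (C) text along these lines:

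*Preterm birth below 37 weeks will also be reported among women still pregnant and below 37w0d, and preterm birth below 34 weeks among women still pregnant and below 34w0d, at the later of first RDV infusion and study entry. Each will show the number at risk and an exact 95% CI, with the same handling of maternal death, terminal fetus/infant events and missing delivery data as the planned proportion.*

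Derive gestational age at that time from the value recorded at 48 hours before first infusion plus elapsed days, and show its distribution beside the results. If only completed weeks are recorded, report the at-risk figure twice, with women recorded at 36 (or 33) weeks counted in and counted out.

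The cost is a short SAP addition, one derived variable, one extra row per cut-off (two if completed weeks are used) and a gestational-age summary, all from data already collected. The downsides are wider intervals on fewer women and a rate that still depends on how long before the cut-off women were treated.
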